#### Laboratory, Vital Sign, and ECG Abnormalities:

Individual stopping rules will be based on repeated measures (single repeat preferably performed within 24 hours of initial result) of the parameters outlined below.

- Grade 3 lymphopenia ( $<500$  cells/mm^3).
- Grade 3 neutropenia ( $<1000$  cells/mm^3).
- Grade 3 ALT/AST ( $>5x$  upper limit of normal (ULN) when not accompanied by an increase in bilirubin).
- Grade 3 bilirubin ( $>2.0$  x ULN when not accompanied by an increase in ALT/AST).
- Changes in liver function tests that meet Hy's Law criteria.
- Serum creatinine  $\geq 1.5$  x ULN.

**Note:** An increase of  $\geq 0.3$  mg/dL (or  $\geq 26.5$   $\mu$ mol/L) in serum creatinine relative to subjects' own baseline measurement should trigger another assessment of SCr within 24-hours from awareness. See [Potential Cases of Acute Kidney Injury](#) for further guidance.

- Grade 2 Hemoglobin  $<10$  g/dL.
- Grade 2 Platelets  $<75,000$ /mm^3 or  $>750,000$ /mm^3.
- 12-lead ECG demonstrating QTc  $\geq 500$ ; or a QRS interval  $\geq 140$  msec or  $\geq 50\%$  increase from baseline; PR interval  $\geq 300$  msec or 25% increase over baseline when baseline  $>200$  msec.

Blood pressure or pulse rate measurements meeting criteria for individual stopping rules should be repeated at least twice, separated by at least 5 minutes, with the subject at rest, supine. If confirmed to be abnormal and confirmed to be clinically significant by investigator, dosing should be stopped and the blood pressure/pulse should be followed

periodically, as deemed appropriate by the investigator, until the blood pressure/pulse rate are returned to within normal limits or deemed acceptable by the investigator.

- Vital sign abnormalities:
  - Systolic blood pressure <90 mmHg or >160 mm Hg;
  - Diastolic blood pressure <50 mmHg or >100 mm Hg;
  - Pulse rate supine/sitting <36 or >120 beats per minute (bpm); standing <36 or >140 bpm.

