**3.4. Individual Stopping Rules for Psoriasis Subjects**

**Treatment with PF-06826647 will be discontinued and the subject withdrawn from this study for:**

**Adverse Events:**

- Serious infections, defined as any infection (viral, bacterial, and fungal) requiring parenteral antimicrobial therapy or hospitalization.
- Other treatment emergent serious or severe AEs, after consultation with the Pfizer clinician.

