**Laboratory, Vital Sign, and ECG Abnormalities:**

Individual stopping rules below will be based on repeated measures (single repeat preferably performed within 24 hours of initial result) of the parameters outlined below.

Laboratory Variable	Laboratory Value
Hematology	
Absolute Neutrophil Count	<1000/mm  ; <1.0 x10  /L
Hemoglobin	<10.0 g/dL; <6.2 mmol/L; <100 g/L
Platelet count	<75,000/mm  ; <75.0x0x10  /L
WBC	<3000/mm  ; <3.0x10  /L
Lymphocytes	<800/mm  ; <0.8x10  /L
Chemistry	
AST	>2.5x ULN
ALT	>2.5x ULN
Creatinine (serum)	>1.5x ULN
Total bilirubin a	>1.5x ULN

a Total bilirubin  $\geq 1.5$  x ULN; subjects with a history of Gilbert's syndrome may have a direct bilirubin measured and would be eligible for this study provided the direct bilirubin is  $\leq$  ULN.

- Changes in liver function tests that meet Hy's Law criteria.

**Note:** An increase of  $\geq 0.3$  mg/dL (or  $\geq 26.5$   $\mu$ mol/L) in serum creatinine relative to subjects' own baseline measurement should trigger another assessment of SCr within 24-hours from awareness. See [Potential Cases of Acute Kidney Injury](#) for further guidance.

- 12-lead ECG demonstrating QTc  $\geq 500$ ; or a QRS interval  $\geq 140$  msec or  $\geq 50\%$  increase from baseline; PR interval  $\geq 300$  msec or 25% increase over baseline when baseline  $> 200$  msec.

Blood pressure measurements meeting criteria for individual stopping rules should be repeated at least twice, separated by at least 5 minutes, with the subject at rest, supine. If confirmed to be abnormal, and confirmed to be clinically significant by investigator, dosing should be stopped and the blood pressure should be followed periodically, as deemed appropriate by the investigator, until the blood pressure are returned to within normal limits or deemed acceptable by the investigator.

- Diastolic: recurrent or persistent ( $\geq 24$  hrs) or symptomatic increase from baseline, in same posture, by  $> 20$  mmHg.
- Systolic: recurrent or persistent ( $\geq 24$  hrs) or symptomatic increase from baseline, in same posture, by  $> 30$  mm Hg.

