#### **4.2. Exclusion Criteria: Healthy Subject Single/Multiple Ascending Dose Cohorts**

Subjects presenting with any of the following characteristics/conditions will not be included in the study:

1. Evidence or history of clinically significant hematological, renal, endocrine, pulmonary, gastrointestinal, cardiovascular, hepatic, psychiatric, neurologic, or allergic disease (including drug allergies, but excluding untreated, asymptomatic, seasonal allergies at time of dosing).
2. Any condition possibly affecting drug absorption (eg, gastrectomy).
3. A positive urine drug screen.
4. History of regular alcohol consumption exceeding 7 drinks/week for females or 14 drinks/week for males (1 drink = 5 ounces (150 mL) of wine or 12 ounces (360 mL) of beer or 1.5 ounces (45 mL) of hard liquor) within 6 months of screening.
5. Treatment with an investigational drug within 30 days (or as determined by the local requirement) or 5 half-lives preceding the first dose of investigational product, whichever is longer.

6. Screening supine blood pressure  $\geq 140$  mm Hg (systolic) or  $\geq 90$  mm Hg (diastolic), following at least 5 minutes of supine rest. If blood pressure (BP) is  $\geq 140$  mm Hg (systolic) or  $\geq 90$  mm Hg (diastolic), the BP should be repeated two more times and the average of the three BP values should be used to determine the subject's eligibility.
7. 12-lead ECG demonstrating QTc  $> 450$ , or a QRS interval  $> 120$  msec at Screening. If QTc exceeds 450 msec, or QRS exceeds 120 msec, the ECG should be repeated two more times and the average of the three QTc (or QRS) values should be used to determine the subject's eligibility.
8. Subjects with **ANY** of the following abnormalities in clinical laboratory tests at screening, as assessed by the study-specific laboratory and confirmed by a single repeat, if deemed necessary:
  - Serum creatinine level above the upper limit of normal or an estimated Glomerular Filtration Rate (GFR) value  $\leq 80$  mL/min, based on the Cockcroft-Gault calculation, at Screening (see [Appendix 2](#)).
  - Aspartate aminotransferase (AST)/serum glutamic oxaloacetic transaminase (SGOT) or alanine aminotransferase (ALT)/serum glutamic pyruvic transaminase (SGPT)  $\geq$  values more than 1.5 times the upper limit of normal.
  - Fasting glucose  $> 110$  mg/dL.
  - Total bilirubin  $\geq 1.5$  x ULN.

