13. Have any condition possibly affecting oral drug absorption, gastrectomy, or clinically significant diabetic gastroenteropathy.
14. History of regular alcohol consumption exceeding 7 drinks/week for females or 14 drinks/week for males (1 drink = 5 ounces (150 mL) of wine or 12 ounces (360 mL) of beer or 1.5 ounces (45 mL) of hard liquor) within 6 months of Screening.
15. 12-lead ECG demonstrating QTc >450, or a QRS interval >120 msec msec at Screening. If QTc exceeds 450 msec or QRS exceeds 120 msec, the ECG should be repeated two more times and the average of the three QTc (or QRS) values should be used to determine the subject's eligibility.

16. Screening supine blood pressure  $\geq 160$  mm Hg (systolic) or  $\geq 100$  mm Hg (diastolic), following at least 5 minutes of supine rest. If blood pressure (BP) is  $\geq 160$  mm Hg (systolic) or  $\geq 100$  mm Hg (diastolic), the BP should be repeated two more times and the average of the three BP values should be used to determine the subject's eligibility.
17. Herbal supplements and hormone replacement therapy must be discontinued 28 days prior to the first dose of study medication. As an exception, acetaminophen/paracetamol may be used at doses of  $\leq 1$  g/day. Limited use of non-prescription medications that are not believed to affect subject safety or the overall results of the study may be permitted on a case-by-case basis following approval by the sponsor.
18. Donated blood in excess of 500 mL (excluding plasma donations) within 2 months prior to the first dose of study drug.
19. Acute disease state (eg, nausea, vomiting, fever, or diarrhea) within 7 days of Day 1.
20. Have a first-degree relative with a hereditary immunodeficiency.
21. Have any malignancies or have a history of malignancies with the exception of adequately treated or excised non-metastatic basal cell or squamous cell cancer of the skin.
22. Have undergone significant trauma or major surgery within 4 weeks of Screening.
23. Are known to be infected with human immunodeficiency virus (HIV) or hepatitis B or C viruses.
24. Have participated in any other studies with JAK inhibitors within 3 months prior to dosing.
25. In the opinion of the investigator or Pfizer, will be uncooperative or unable to comply with study procedures.
26. Have participated in other studies involving investigational drug(s) within 30 days or 5 half-lives (whichever is longer) prior to study entry and/or during study participation.

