### 8.3. Severity Assessment

If required on the AE page of the CRF, the investigator will use the adjectives MILD, MODERATE, or SEVERE to describe the maximum intensity of the AE. For purposes of consistency, these intensity grades are defined as follows:	
MILD	Does not interfere with subject's usual function.
MODERATE	Interferes to some extent with subject's usual function.
SEVERE	Interferes significantly with subject's usual function.

Note the distinction between the severity and the seriousness of an AE. A severe event is not necessarily an SAE. For example, a headache may be severe (interferes significantly with the subject's usual function) but would not be classified as serious unless it met one of the criteria for SAEs, listed above.

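### The psoriasis blood-pressure stopping rule is relative to baseline only, so a sustained asymptomatic 189/119 mmHg from the entry limit of 159/99 never triggers it; an absolute backstop is a cheap addition

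*Protocol*

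**What the plan says.** **Psoriasis subjects (Protocol Section 3.4).** There are two blood-pressure criteria, both measured as a change. Each requires a recurrent, persistent (24 hours or more) or "symptomatic increase from baseline, in same posture, by" more than 20 mmHg (diastolic) or more than 30 mmHg (systolic). The procedure attached to them is: "Blood pressure measurements meeting criteria for individual stopping rules should be repeated at least twice, separated by at least 5 minutes". If the value is confirmed as abnormal and the investigator finds it clinically significant, dosing stops.

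**Healthy subjects (Section 3.3).** The criteria are absolute: "Systolic blood pressure <90 mmHg or >160 mm Hg" and "Diastolic blood pressure <50 mmHg or >100 mm Hg". The repeat procedure and the investigator's judgement of clinical significance are the same.

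**Entry.** Psoriasis exclusion 16 (Section 4.4, "16. Screening supine blood pressure") excludes at 160/100 mmHg or above. Healthy exclusion 6 (Section 4.2, "6. Screening supine blood pressure") excludes at 140/90 or above.

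**Other routes to stopping in psoriasis.** Section 3.4 also lists "Other treatment emergent serious or severe AEs, after consultation with the Pfizer clinician". Section 6.4 allows withdrawal for safety at the discretion of the investigator or sponsor. Neither carries a blood-pressure value.

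**The concern.** A purely relative rule has no fixed ceiling: the higher the baseline, the higher the pressure it tolerates. That matters most where high baselines are admitted, and the psoriasis cohorts admit pressures 20/10 mmHg above the healthy limit and dose for 28 days rather than 10. Vital signs, including blood pressure, are a primary safety endpoint in these cohorts (Section 2).

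The protocol does not avoid absolute limits as a matter of principle. Section 3.3 uses them for blood pressure. The ECG rule in Section 3.4 itself pairs absolute with relative limits (QRS at or above 140 msec or a 50% increase; PR at or above 300 msec or a 25% increase when baseline exceeds 200 msec). Blood pressure in psoriasis is the exception.

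The adverse-event route does not reliably close the gap. Section 8.3 grades severity by effect on function, with mild defined as "Does not interfere with subject's usual function", so a symptomless rise would not by itself grade as severe. Treating it as serious would need a judgement that it is an important medical event.

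**Working it through.** The plan gives no figure to reproduce. The check applies the written thresholds.

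**Inputs**
- Highest whole-mmHg entry value: psoriasis 159/99 (Section 4.4, exclusion 16); healthy 139/89 (Section 4.2, exclusion 6).
- Psoriasis stop: rise strictly above 30 systolic or 20 diastolic (Section 3.4).
- Healthy stop: strictly above 160 systolic or 100 diastolic (Section 3.3).
- Baseline: last pre-dose value (SAP Section 6), taken here as equal to the screening maximum.

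**Step 1. Highest non-triggering pressure = baseline + 30 / baseline + 20.**
159 + 30 = 189 and 99 + 20 = 119. The rise is exactly 30/20, which is not above 30/20. The first qualifying values are 190 systolic (rise 31) or 120 diastolic (rise 21).

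**Step 2. Excess over the healthy limits at the entry limit.**
189 − 160 = 29; 119 − 100 = 19 mmHg.

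**Step 3. Baseline at which the two rules cross.**
160 − 30 = 130 systolic; 100 − 20 = 80 diastolic. Above these the psoriasis rule is looser, below them tighter:

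| Baseline | Highest pressure not triggering the psoriasis rule | Against the healthy limit 160/100 |
|---|---|---|
| 120/75 | 150/95 | tighter by 10/5 |
| 130/80 | 160/100 | equal |
| 139/89 | 169/109 | looser by 9/9 |
| 150/95 | 180/115 | looser by 20/15 |
| 159/99 | 189/119 | looser by 29/19 |

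**Step 4. A backstop value on the protocol's own scale.**
The healthy stop lies 160 − 140 = 20 and 100 − 90 = 10 mmHg above the healthy exclusion limit. The same step from the psoriasis exclusion limit gives 160 + 20 = 180 and 100 + 10 = 110. It would bind only where the relative rule allows more: baselines above 180 − 30 = 150 systolic or 110 − 20 = 90 diastolic. At the entry limit it lowers the ceiling by 189 − 180 = 9 and 119 − 110 = 9 mmHg. Headroom at entry then matches the healthy rule: 180 − 159 = 21 and 110 − 99 = 11, against 160 − 139 = 21 and 100 − 89 = 11.

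**Step 5. How many subjects start in that region.**
Baseline pressures are not in the documents, so these are assumptions: normal distributions truncated at the exclusion limit.

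| Assumption | Threshold | Share starting above it |
|---|---|---|
| Systolic mean 120–135, SD 12–15, cut at 160 | 130 (looser than healthy limit) | 20%–66% |
| Same | 150 (backstop binds) | 0.6%–12% |
| Diastolic mean 75–84, SD 8–10, cut at 100 | 80 (looser than healthy limit) | 27%–68% |
| Same | 90 (backstop binds) | 3%–23% |

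These are shares of starting pressures only. They do not estimate how many subjects would also have a rise that falls between the two limits.

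**The case against.** **The healthy rule does not stop dosing on confirmation.** A reader might infer that healthy subjects get an automatic stop and psoriasis subjects only a discretionary one. The documents do not support that. Section 3.3 also requires the investigator to find the value clinically significant. What differs is whether a fixed number starts the process.

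**The psoriasis rule is not generally looser.** This stands: below 130/80 it triggers earlier. From 120/75 it triggers at 151 or 96, against 161 or 101 for healthy subjects.

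**A relative rule suits subjects with raised baseline pressure.** This also stands. Importing 160/100 would put the trigger 1–2 mmHg above permitted entry values. It is a reason to keep the relative criteria, not a reason to have no ceiling.

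**Does dosing continue by default for 24 hours after a first confirmed rise?** A reader might infer this, since a first asymptomatic rise has not yet lasted 24 hours. The text does not establish it. Recurrence is undefined and could cover elevation found again on repeat, and a 5-minute repeat would have little purpose if nothing could qualify before 24 hours. The point does not rest on this reading.

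**Risk is low and supervision close.** Largely true. Section 1.2.4 reports rat diastolic and mean pressure up 3 mmHg at 500 mg/kg and no cardiovascular change in monkeys. Section 1.3.2 reports 53 healthy subjects treated with drug or placebo, no Section 3.3 stopping criterion met and all adverse events mild. Psoriasis dosing follows review of 10-day data from at least 6 healthy subjects at the equivalent once-daily dose, and subjects are housed through Day 28. An investigator worried by 189/119 can withdraw the subject under Section 6.4. That lowers the urgency, but healthy subjects have the same discretion and still receive absolute limits.

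**159/99 is a corner case.** It is. However, exclusion 16 applies at screening while the rise is measured from the last pre-dose value, and no Day −1 pressure limit is set for psoriasis subjects. So 189/119 is not a firm upper bound either.

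**Conclusion.** The gap is real and narrow. Section 3.4 has no absolute blood-pressure ceiling, and at the permitted entry limit a sustained asymptomatic 189/119 never reaches the repeat-and-judge step. That is 29/19 mmHg above the values that start the same step in healthy subjects. SAP Section 9.4 would list such a rise (30 or more systolic, 20 or more diastolic) as of potential clinical concern, yet the stopping rule would not respond to it.

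The size depends on baseline: the psoriasis rule is looser only above 130 systolic or 80 diastolic. The 189/119 figure assumes a baseline equal to the screening maximum on both components. The population shares rest on assumed means and SDs.

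This is a low-priority safety backstop, worth adding because it is cheap. It is not evidence that psoriasis subjects are unprotected.

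**What to change.** Keep both relative bullets in Section 3.4 and add one: supine systolic above 180 mmHg or diastolic above 110 mmHg, confirmed by the two repeats already specified, with no persistence requirement and subject to the same investigator judgement of clinical significance. The value 180/110 carries Section 3.3's own 20/10 step over to the psoriasis exclusion limit; the sponsor may choose a lower one.

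Do not add a companion sentence saying that dosing may continue below that value while recurrence or persistence is assessed. It would expressly permit dosing after, for example, a confirmed asymptomatic change from 120/75 to 178/108, a rise of 58/33. The current text gives no such permission.

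**Cost.** One bullet, with no extra readings or visits. There may be a few extra withdrawals, limited to confirmed readings above the ceiling that the investigator judges significant. Each would lose that subject's later PK and possibly the Day 28 PASI. Section 6.4 already allows psoriasis subjects who discontinue early to be replaced.

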**Other:**

- Subjects non-compliant with study treatment.

### **3.5. Discontinuation/End of Treatment Monitoring for Adverse Events, Laboratory, Vital Signs and ECG Abnormalities**

Any subject meeting discontinuation criteria will be followed up every 1 to 2 weeks, with retesting as appropriate, until the event has returned to normal or baseline levels or is deemed clinically stable.

Additional follow-up visits may occur as needed until any clinically relevant abnormalities or adverse events have resolved, returned to a baseline state, or are deemed clinically stable.

## **4. SUBJECT ELIGIBILITY CRITERIA**

This study can fulfill its objectives only if appropriate subjects are enrolled. The following eligibility criteria are designed to select subjects for whom participation in the study is considered appropriate. All relevant medical and nonmedical conditions should be taken into consideration when deciding whether a particular subject is suitable for this protocol.

### **4.1. Inclusion Criteria: Healthy Subject Single/Multiple Ascending Dose Cohorts**

Subject eligibility should be reviewed and documented by an appropriate member of the investigator's study team before subjects are included in the study.

Subjects must meet all of the following inclusion criteria to be eligible for enrollment into the study:

1. Healthy female subjects of non-childbearing potential and/or male subjects between the ages of 18 and 55 years, inclusive (Healthy is defined as no clinically relevant abnormalities identified by a detailed medical history, full physical examination, including blood pressure and pulse rate measurement, 12-lead ECG and clinical laboratory tests).
2. Female subjects of non-childbearing potential must meet at least 1 of the following criteria:
  - a. Achieved postmenopausal status, defined as follows: cessation of regular menses for at least 12 consecutive months with no alternative pathological or physiological cause; and have a serum follicle-stimulating hormone (FSH) level confirming the post-menopausal state.
  - b. Have undergone a documented hysterectomy and/or bilateral oophorectomy.
  - c. Have medically confirmed ovarian failure.

All other female subjects (including females with tubal ligations ) are considered to be of childbearing potential.

3. Body Mass Index (BMI) of 17.5 to 30.5 kg/m^2; and a total body weight >50 kg (110 lbs).

4. Evidence of a personally signed and dated informed consent document indicating that the subject has been informed of all pertinent aspects of the study.
5. Subjects who are willing and able to comply with scheduled visits, treatment plan, laboratory tests, and other study procedures.
6. No evidence of active or latent or inadequately treated infection with *Mycobacterium tuberculosis* (TB) as defined by the following:
  - a. negative Interferon Gamma Release Assay (IGRA) (with the following acceptable assays: QuantiFERONR-TB Gold (QFT-G) test, T-SPOT TB, QuantiFERON-TB Gold In-Tube test (QFT-GIT)) performed during Screening or within 3 months prior to Day 1.

AND

- b. No history of either untreated or treated latent or active TB infection.

A subject who is currently being treated for either latent or active TB infection is to be excluded.

7. Additional criterion for subjects to be enrolled in Japanese cohort only: Japanese subjects who have four Japanese biologic grandparents born in Japan.

#### **4.2. Exclusion Criteria: Healthy Subject Single/Multiple Ascending Dose Cohorts**

Subjects presenting with any of the following characteristics/conditions will not be included in the study:

1. Evidence or history of clinically significant hematological, renal, endocrine, pulmonary, gastrointestinal, cardiovascular, hepatic, psychiatric, neurologic, or allergic disease (including drug allergies, but excluding untreated, asymptomatic, seasonal allergies at time of dosing).
2. Any condition possibly affecting drug absorption (eg, gastrectomy).
3. A positive urine drug screen.
4. History of regular alcohol consumption exceeding 7 drinks/week for females or 14 drinks/week for males (1 drink = 5 ounces (150 mL) of wine or 12 ounces (360 mL) of beer or 1.5 ounces (45 mL) of hard liquor) within 6 months of screening.
5. Treatment with an investigational drug within 30 days (or as determined by the local requirement) or 5 half-lives preceding the first dose of investigational product, whichever is longer.

6. Screening supine blood pressure  $\geq 140$  mm Hg (systolic) or  $\geq 90$  mm Hg (diastolic), following at least 5 minutes of supine rest. If blood pressure (BP) is  $\geq 140$  mm Hg (systolic) or  $\geq 90$  mm Hg (diastolic), the BP should be repeated two more times and the average of the three BP values should be used to determine the subject's eligibility.
7. 12-lead ECG demonstrating QTc  $> 450$ , or a QRS interval  $> 120$  msec at Screening. If QTc exceeds 450 msec, or QRS exceeds 120 msec, the ECG should be repeated two more times and the average of the three QTc (or QRS) values should be used to determine the subject's eligibility.
8. Subjects with **ANY** of the following abnormalities in clinical laboratory tests at screening, as assessed by the study-specific laboratory and confirmed by a single repeat, if deemed necessary:
  - Serum creatinine level above the upper limit of normal or an estimated Glomerular Filtration Rate (GFR) value  $\leq 80$  mL/min, based on the Cockcroft-Gault calculation, at Screening (see [Appendix 2](#)).
  - Aspartate aminotransferase (AST)/serum glutamic oxaloacetic transaminase (SGOT) or alanine aminotransferase (ALT)/serum glutamic pyruvic transaminase (SGPT)  $\geq$  values more than 1.5 times the upper limit of normal.
  - Fasting glucose  $> 110$  mg/dL.
  - Total bilirubin  $\geq 1.5$  x ULN.
  - A white blood cell count below  $4.5 \times 10^3/\text{mm}^3$ , including history of benign ethnic neutropenia. Subjects with borderline clinical laboratory values outside the reference range may be included in the study if the investigator deems that the values are not clinically significant.
  - Absolute neutrophil count of  $< 2 \times 10^9/\text{L}$  ( $< 2000/\text{mm}^3$ ).
  - Hematocrit below 38% for males and 33% for females. Subjects with borderline clinical laboratory values outside the reference range may be included in the study if the investigator deems that the values are not clinically significant.
  - Red blood cell and reticulocytes outside the reference range at screening. Subjects with borderline clinical laboratory values outside the reference range may be included in the study if the Investigator deems that the values are not clinically significant.
  - Platelet counts below LLN. Subjects with borderline clinical laboratory values outside the reference range may be included in the study if the investigator deems that the values are not clinically significant.

9. Any medical history of disease that has the potential to cause a rise in total bilirubin over the upper limit of normal (ULN). Subjects with borderline clinical laboratory values outside the reference range may be included in the study if the investigator deems that the values are not clinically significant.

**Note:** Subjects with a history of Gilbert's syndrome may have a direct bilirubin measured and would be eligible for this study provided the direct bilirubin is  $\leq$  ULN.

10. Pregnant female subjects; breastfeeding female subjects; female subjects of childbearing potential.
11. Fertile male subjects who are unwilling or unable to use a highly effective method of contraception as outlined in this protocol for the duration of the study and for at least 28 days after the last dose of investigational product.
12. Herbal supplements and hormone replacement therapy must be discontinued 28 days prior to the first dose of study medication. As an exception, acetaminophen/paracetamol may be used at doses of  $\leq 1$  g/day. Limited use of non-prescription medications that are not believed to affect subject safety or the overall results of the study may be permitted on a case-by-case basis following approval by the sponsor.
13. Use of prescription or nonprescription drugs and dietary supplements within 7 days or 5 half-lives (whichever is longer) prior to the first dose of study medication. As an exception, acetaminophen/paracetamol may be used at doses of  $\leq 1$  g/day. Limited use of nonprescription medications that are not believed to affect subject safety or the overall results of the study may be permitted on a case by case basis following approval by the sponsor.
14. Blood donation (excluding plasma donations) of approximately 1 pint (500 mL) or more within 56 days prior to dosing.
15. History of sensitivity to heparin or heparin-induced thrombocytopenia.
16. Unwilling or unable to comply with the [Lifestyle Requirements \(Section 4.6\)](#) described in this protocol.
17. Other severe acute or chronic medical or psychiatric condition including recent (within the past year) or active suicidal ideation or behavior or laboratory abnormality that may increase the risk associated with study participation or investigational product administration or may interfere with the interpretation of study results and, in the judgment of the investigator, would make the subject inappropriate for entry into this study.

18. Subjects who are investigator site staff members directly involved in the conduct of the study and their family members, site staff members otherwise supervised by the investigator, or subjects who are Pfizer employees including their family members directly involved in the conduct of the study.
19. Will have vaccination with live virus, attenuated live virus, or any live viral components within the 6 weeks prior to the first dose of study drug or is to receive these vaccines at any time during treatment or within 8 weeks following completion of study treatment.
20. Have a history of any lymphoproliferative disorder (such as Epstein Barr Virus [EBV]-related lymphoproliferative disorder, as reported in some subjects on other immunosuppressive drugs), history of lymphoma, leukemia, myeloproliferative disorders, multiple myeloma, or signs and symptoms suggestive of current lymphatic disease.
21. Have a clinically significant infection currently or within 6 months of first dose of study drug (eg, those requiring hospitalization or parenteral antimicrobial therapy or opportunistic infections), or a history of chronic or recurrent infectious disease.
22. Have or have had symptomatic herpes zoster or herpes simplex within 12 weeks, more than one episode of local herpes zoster, or a history (single episode) of disseminated zoster.
23. Are known to be infected with human immunodeficiency virus (HIV) or hepatitis B or C viruses.
24. Subjects with a history of cancer with the exception of adequately treated basal cell or squamous cell carcinoma of the skin.
25. Acute disease state (eg, nausea, vomiting, fever, or diarrhea) within 7 days of Day 1.
26. Have a first-degree relative with a hereditary immunodeficiency.
27. Have undergone significant trauma or major surgery within 4 weeks of Screening.
28. Use of tobacco/nicotine containing products in excess of  $\geq 5$  cigarettes/day.
29. Consumption of grapefruit or grapefruit juice or citrus fruits eg, Seville oranges, pomelos within 7 days prior to the first dose of study medication until collection of the final pharmacokinetic blood sample.
30. Subjects who received (within 4 weeks of first dose of PF-06826647) or were likely to receive during the study any of the medications listed in protocol [Appendix 3](#).

